6.3 Implementation of the Copy Increment from Reference and Pattern Mixture Model

6.3.1 Copy Increment from Reference

The dataset will first be imputed to monotone missing using PROC MI with the MCMC and impute=monotone option. Imputation will be carried out 1000 times and any internal missing observations, including missing baseline covariates and intermediate missing in the response variable will be replaced with the average across all imputations.

For the resulted data with monotone missing, the following steps will be used to create imputed datasets:

- (1) Data from all patients will be used to fit a multivariate normal distribution with unstructured mean and unstructured variance using a Bayesian approach with a noninformative prior for the mean and a conjugate prior for the variance covariance matrix.
- (2) Draw a pseudo-independent sample for the linear predictor parameters and the covariance parameters from the joint posterior distribution obtained in step (1). Both steps (1) and (2) will be done using PROC MCMC in SAS.
- (3) Use the linear predictor parameters and the covariance parameters obtained in step (2) to construct new mean vectors separately for each treatment group (placebo, aducanumab low dose, aducanumab high dose). Specifically, the newly constructed mean vector for someone on treatment group *T* whose last observed visit was visit *k* is calculated as

$$\mu_{T}^{(k)} = \{ \begin{aligned} \mu_{i,T}, & \text{if } i \leq k \\ \mu_{k,T} - \mu_{k,P} + \mu_{i,P}, & \text{if } i > k \end{aligned} \end{aligned}$$

Here *P* represents the placebo group. For patients with no post-baseline records, or patients on the placebo group, the newly constructed mean vector is the same as the placebo mean.

(4) Using $\mu_T^{(k)}$ from step (3) and covariance parameters from step (2), find the conditional normal distribution of the visit with missing data, and use this conditional distribution to impute the missing data.

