4.3.2.2.1 Pattern mixture model

The pattern mixture model (PMM) represents a general and flexible framework to model the predictive distribution of missing data conditional on the observed data [Little 1993, 1994]. It allows formulating assumptions regarding missing data in a transparent and clinically interpretable manner.

In the PMM framework, subjects are grouped into missing patterns so that subjects in the same pattern share similar missingness characteristics. In this analysis, missing patterns will be defined according to the reasons for early withdrawal from study as reported on the electronic case report form (eCRF). The following two patterns will be considered:

- Subjects who withdraw due to reasons that may be related to efficacy, including consent withdrawn, withdrawal by parent/guardian, investigator decision, loss of capacity, change of treatment, and disease progression;
- Subjects who withdraw due to reasons that are unlikely related to efficacy, including adverse event, lost to follow-up, death, pregnancy, relocation, protocol amendment, site terminated by sponsor/investigator, study visit burden, and other.

Subjects who withdraw due to reasons that may be related to efficacy will be penalized and their missing data will be imputed using the copy increment from reference (CIR) method [Carpenter et al. 2013] (see Section 4.3.2.2.2 for description of the CIR method). Subjects who withdraw due to reasons that are unlikely related to efficacy will be handled using the missing-at-random assumption and their missing data will be imputed using the standard multiple imputation method [Rubin 1987]. Subjects with missing data due to reasons other than early withdrawal (such as item missing, out of window, etc.) will be handled using the missing-at-random assumption. For both imputation methods, the following covariates will be included in the imputation model: treatment group, baseline CDR-SB, baseline MMSE, AD symptomatic medication use at baseline (yes/no), region, and laboratory ApoE £4 status (carrier/non-carrier). Implementation details can be found in Appendix 6.3.2.

The imputed datasets will be analyzed by an analysis of covariance (ANCOVA) model adjusting treatment group, baseline CDR-SB, baseline MMSE, AD symptomatic medication use at baseline (yes/no), region, and laboratory ApoE & status (carrier/non-carrier). The analyzed results from the imputed datasets will be combined based on Rubin's rules [Rubin

Final V1.0

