1987] assuming that the statistics estimated from each imputed dataset are normally distributed.

If intermediate missing values are encountered (such as data missing at Week 26 but are available at subsequent visits), a Markov chain Monte Carlo (MCMC) method that assumes multivariate normality will be used to impute the intermediate missing values and produce a monotone missing pattern (data with only terminal missing and no intermediate missing) [Li 1988; Schafer 1997].

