4.3.2.2.2 Copy increment from reference method

The copy increment from reference (CIR) method will be applied to impute the post-withdrawal data for any aducanumab-treated subject who withdraws from study early based on data from the placebo group rather than the subject's own randomized treatment group [Carpenter et al. 2013]. Specifically, for a subject on aducanumab high dose (or aducanumab low dose) who withdraws early, his or her mean trajectory after early withdrawal is assumed to be parallel to the mean trajectory of the placebo group, and the difference between the two means is the same as the difference at the time of withdrawal. This method assumes that any benefit gained from previous treatment will be retained, but subjects progress as if they were on placebo after withdrawal from study. For any subject on placebo who withdraws early, his or her post-withdrawal profile will be imputed following the missing-at-random principle. Implementation details can be found in Appendix 6.3.1.

After all missing data have been imputed, an ANCOVA model adjusting treatment group, baseline CDR-SB, baseline MMSE, AD symptomatic medication use at baseline (yes/no), region, and laboratory ApoE ε4 status (carrier/non-carrier) will be applied to analyze the change from baseline CDR-SB.

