6.3.2 Pattern Mixture Model

Subjects will be assigned one of the following three patterns:

Final V1.0

- 1. Completer: subjects with no missing data at Week 26, 50 and 78
- 2. Subjects who withdrew due to reasons that may be related to efficacy, including consent withdrawn, withdrawal by parent/guardian, investigator decision, loss of capacity, change of treatment, and disease progression;
- 3. All the other subjects with missing data.

The dataset will first be imputed to monotone missing using PROC MI with the MCMC and impute=monotone option. Imputation will be carried out 1000 times and any internal missing observations, including missing baseline covariates and intermediate missing in the response variable will be replaced with the average across all imputations.

For the resulted data with monotone missing, the following steps will be used to create imputed datasets:

- (1) Subset subjects in pattern 1 and pattern 2, and impute the missing data using the copy increment from reference method described in Section 6.3.1.
- (2) Subset subjects in pattern 1 and pattern 3, and impute the missing data using PROC MI with the MONOTONE REG option.
- (3) Combined datasets obtained in steps (1) and (2).

Final V1.0

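### The CIR and pattern mixture analyses fill intermediate gaps and missing covariates with the mean of 1000 imputations and then treat them as observed: improper, but with negligible expected effect on the standard error and only a small possible bias

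*SAP*

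**What the plan says.** - SAP 6.3.1 (CIR) first makes the data monotone by MCMC. It does not keep the draws: each missing baseline covariate and "intermediate missing in the response variable will be replaced with the average across all imputations".
- SAP 6.3.2 (pattern mixture model) repeats the rule: "Imputation will be carried out 1000 times and any internal missing observations, including missing baseline covariates and" intermediate scores receive the average.
- The second stage starts from that single dataset: "For the resulted data with monotone missing, the following steps will be used to create imputed datasets". Only terminal gaps are drawn repeatedly after this.
- SAP 4.3.2.2.1 describes the same step without averaging; MCMC is "used to impute the intermediate missing values and produce a monotone missing pattern". It gives as an example "data missing at Week 26 but are available at subsequent visits".
- Pooling is explicit for the pattern mixture model: "The analyzed results from the imputed datasets will be combined based on Rubin's rules" (4.3.2.2.1). For CIR, 4.3.2.2.2 says only "After all missing data have been imputed, an ANCOVA model adjusting treatment group, baseline CDR-SB, baseline MMSE" and the other covariates; it names no pooling rule.
- Both are sensitivity analyses for departures from missing at random (4.3.2.2). The pattern mixture model is the only analysis labelled as a sensitivity analysis for the three secondary endpoints (Table 2; 4.3.3.4).

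**The concern.** The mean of 1000 draws is, in effect, the conditional expectation given the subject's observed data: one value without residual noise. Rubin's rules need each dataset to carry its own draw. Here every dataset holds the same filled values, so they contribute nothing to the between-imputation variance.

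There is a second effect. An intermediate gap at Week 50 is filled partly from the subject's own Week 78 score. That keeps the covariance of Week 50 with Week 78 but shrinks the variance of Week 50. The regression that then imputes dropouts is too steep, and its residual variance is too small.

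Third, the average of a yes/no or three-level covariate is a value in no category, and the SAP does not say how it would enter the model.

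At stake is the soundness of two planned stress tests of the missing-data assumption, not the primary result.

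**Working it through.** **Inputs from the SAP.** Section 3: SD 1.92 at Week 78, difference 0.5, dropout 30%, 450 per group raised to 535, two-sided 0.05. The sample size reproduces: 2 × (1.960 + 1.282)² × 1.92² / 0.5² = 310 evaluable per group, and 310 / 0.7 = 443, close to the stated 450. The SAP states no standard error for these two analyses and no rate of intermediate missingness.

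**Assumptions for the slope.** SDs 1.1 and 1.5 at Weeks 26 and 50; correlations 0.6 (Weeks 26-50), 0.7 (50-78), 0.5 (26-78). A fraction p of subjects lacks Week 26 only, and another fraction p lacks Week 50 only.

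1. Covariances: C(26,50) = 0.6 × 1.1 × 1.5 = 0.990; C(50,78) = 0.7 × 1.5 × 1.92 = 2.016; C(26,78) = 0.5 × 1.1 × 1.92 = 1.056. Conditional-mean filling leaves these unchanged.
2. Week 50 slope = [C(50,78) × V26 − C(26,78) × C(26,50)] / [V26 × V50 − C(26,50)²]. With complete data, V26 = 1.21 and V50 = 2.25: 1.394 / 1.742 = 0.800.
3. Filled values keep only the explained share of their variance. R² is 0.373 for Week 26 given Weeks 50 and 78, and 0.573 for Week 50 given Weeks 26 and 78. So V26 becomes 1.21 × (1 − 0.627p) and V50 becomes 2.25 × (1 − 0.427p).
4. At p = 5%, V26 = 1.172 and V50 = 2.202: slope 1.317 / 1.601 = 0.823, which is 2.9% too steep.
5. At p = 10%, V26 = 1.134 and V50 = 2.154: slope 1.241 / 1.463 = 0.848, which is 6.0% too steep.

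Adjacent-visit correlations of 0.6-0.8, with 0.45-0.6 for Weeks 26-78, give much the same picture: about 2.5-6%, or about 7% for some combinations at p = 10%. The imputation model's residual variance is about 2-5% too small.

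**Effect on the pooled standard error.** The appendix algorithm was simulated with 535 per arm, 30% dropout, 120 trials per scenario and 200 imputations. Assumed: SDs 1.20, 1.55 and 1.92; correlations 0.6, 0.5 and 0.7; baseline MMSE missing in 1, 2 and 5%. For the pattern mixture model, half the dropouts were imputed by CIR and half at random, fitted on all data.

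| Subjects with an intermediate gap | CIR SE, separate draws / averaged | CIR ratio | Pattern mixture SE, separate / averaged | Ratio |
|---|---|---|---|---|
| 7.5% | 0.1237 / 0.1239 | 1.001 | 0.1247 / 0.1247 | 1.000 |
| 14% | 0.1239 / 0.1237 | 0.998 | 0.1249 / 0.1246 | 0.998 |
| 27% | 0.1239 / 0.1240 | 1.000 | 0.1248 / 0.1248 | 1.000 |

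Monte Carlo error of the ratios is about 0.001. In this simulation the point estimates agree within 0.001. A separate simulation of the missing-at-random stage, at 5-20% intermediate missing per visit, gave ratios of 0.999-1.002 (error about 0.002). There the between-imputation variance was up to 4-5% too small, offset by a within-imputation variance up to about 1% too large.

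**Effect on the estimate.** A dropout's Week 78 score is imputed as the mean plus slope × (own Week 50 score − mean). An excess slope therefore matters only if dropouts' Week 50 scores lie at different distances from their arm means in the two arms. As an illustration, take that between-arm difference as 1 point and put all 30% dropout after Week 50. The shift is 0.30 × (0.823 − 0.800) × 1 = 0.007 at p = 5% and 0.30 × (0.848 − 0.800) × 1 = 0.014 at p = 10%, before a partial offset from a lower Week 26 slope. Simulation with dropout depending on Week 50 differently by arm, at 5-20% intermediate missing, moved the Week 78 difference by about 0.003-0.024 points relative to separate draws. The upper end is 0.024 / 0.5 = 4.8% of the planned effect.

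**The case against.** A reader might infer that the CIR and pattern mixture standard errors are too small by construction, and increasingly so as gaps accumulate. The results do not support that. An intermediate gap has a later visit observed, so the Week 78 outcome is never replaced by an average; missing Week 78 scores are still drawn. The averaged values act only through the imputation model and covariate adjustment. A further set of 500 simulated trials gave standard error ratios of 0.9987, 0.9983 and 0.9990 at 5, 10 and 15% intermediate missing. A control with nothing missing gave 1.001, so the departures are about the size of the noise and show no trend. Nor does the averaged-method standard error fall below the empirical SD of the estimate: about 0.124 against 0.106-0.107 for CIR, and 0.125 against 0.118 for the pattern mixture model. With 120 trials the SD carries a relative error of about 1/√(2 × 119) = 6.5%, so only the CIR gap is clear.

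The SAP also limits the problem. Visit windows are contiguous, unscheduled visits are mapped in, and missing items are prorated (4.3.1). Baseline AD medication use is derived from medication records (4.2.3), so a missing yes/no value there is unlikely. A fractional covariate does harm only if such a value is missing and depending on how it is coded, and the SAP states neither.

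All of this stands, and it limits the size of the point. It does not make the averaging step proper: the step remains written twice in the appendix and absent from the main text.

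**Conclusion.** The point holds as a minor methodological flaw. The plan states a deterministic single imputation for intermediate scores and missing covariates, whose uncertainty never reaches the pooling step. Rubin's rules are stated for the pattern mixture model and only implied for CIR.

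The net effect on the pooled standard error is negligible, about 0.2% or less, with direction not established. The more relevant consequence is the too-steep Week 50 slope and the small bias that it can cause under arm-dependent dropout.

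These sizes rest on assumed correlations, SDs, dropout patterns and intermediate-missing rates, and on the CDR-SB scale. Categorical covariates and the pattern-subset fits of 6.3.2 were not simulated. If laboratory ApoE status, for example, is missing, its average is not a valid category; how often that happens is unknown. The primary MMRM uses observed data and is untouched. A changed conclusion is unlikely.

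**What to change.** In SAP 6.3.1 and 6.3.2:

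- Delete the averaging step. Run PROC MI with MCMC and impute=monotone once per final imputation, so that there are as many monotone datasets as completed datasets.
- Complete each monotone dataset once, by CIR or MONOTONE REG as its pattern requires, and analyse each by the planned ANCOVA.
- Pool by Rubin's rules, and say so for CIR in 4.3.2.2.2 as well.
- Impute any missing categorical baseline covariate as a category.

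The cost is a sentence or two in each section and a simpler program. No data collection changes, and the appendix then agrees with 4.3.2.2.1.

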6.3.2 Pattern Mixture Model

Subjects will be assigned one of the following three patterns:

Final V1.0

- 1. Completer: subjects with no missing data at Week 26, 50 and 78
- 2. Subjects who withdrew due to reasons that may be related to efficacy, including consent withdrawn, withdrawal by parent/guardian, investigator decision, loss of capacity, change of treatment, and disease progression;
- 3. All the other subjects with missing data.

The dataset will first be imputed to monotone missing using PROC MI with the MCMC and impute=monotone option. Imputation will be carried out 1000 times and any internal missing observations, including missing baseline covariates and intermediate missing in the response variable will be replaced with the average across all imputations.

For the resulted data with monotone missing, the following steps will be used to create imputed datasets:

- (1) Subset subjects in pattern 1 and pattern 2, and impute the missing data using the copy increment from reference method described in Section 6.3.1.
- (2) Subset subjects in pattern 1 and pattern 3, and impute the missing data using PROC MI with the MONOTONE REG option.
- (3) Combined datasets obtained in steps (1) and (2).

Final V1.0

	3.5.6 ECG Data	
	3.5.7 Vital Sign Data	
	3.6 PHARMACOKINETICS ANALYSIS	
	3.6.1 Serum Concentration Profile	
	3.6.2 Serum PK Parameters	
	3.7 IMMUNOGENICITY ANALYSIS	
	3.7.1 Background	
	3.7.2 Immunogenicity analysis	33
4	APPENDIX	35

Final V1.0

Analysis Display......35

Statistical Analysis Plan

Long-Term Extension Period

Final V1.0

List of Abbreviations

Αβ	β-amyloid				
AD	Alzheimer's disease				
ADAS-Cog 13	Alzheimer's Disease Assessment Scale-Cognitive Subscale				
S	(13 items)				
ADCS-ADL-MCI	Alzheimer's Disease Cooperative Study - Activities of Daily				
	Living Inventory (Mild Cognitive Impairment version)				
ADNI	Alzheimer's Disease Neuroimaging Initiative				
AE	adverse event				
ALP	alkaline phosphatase				
ALT	alanine aminotransferase				
ANCOVA	analysis of covariance				
ApoE	apolipoprotein E				
ΑροΕ ε4	apolipoprotein E4				
ΑροΕ ε4+	apolipoprotein E4 carrier				
ApoE ε4-	apolipoprotein E4 non-carrier				
ARIA	amyloid related imaging abnormalities				
ARIA-E	amyloid related imaging abnormality-edema				
ARIA-H	amyloid related imaging abnormality-hemorrhage or superficial				
	siderosis				
AST	aspartate aminotransferase				
BL	baseline				
BLQ	below the limit of quantification				
BMI	body mass index				
bpm	beats per minute				
BUN	blood urea nitrogen				
CDR	Clinical Dementia Rating				
CDR-SB	Clinical Dementia Rating-Sum of Boxes				
CIR	copy increment from reference				
C_{max}	observed maximum serum aducanumab concentration				
C_{min}	observed minimum serum aducanumab concentration				
CSF	cerebrospinal fluid				
C-SSRS	Columbia Suicide Severity Rating Scale				
CTCAT	Common Toxicity Criteria for Adverse Events				
CV	coefficient of variation				
EAIR	exposure-adjusted incidence rate				
ECG	electrocardiogram				
eCRF	electronic case report form				
EQ-5D EuroQol health status measure					
EQ-5D (IR-S)	EuroQol health status measure, informant reported on subject				
EQ-5D (SR)	EuroQol health status measure, subject self-reported				

ELI	Γ.11			
FU	Follow-up			
GCP	Good Clinical Practice			
GGT	gamma-glutamyl-transferase			
HCP	health care professional			
ICF	informed consent form			
ICH	International Conference on Harmonisation			
IDMC	independent data monitoring committee			
IRB	institutional review board			
IRT	interactive response technology			
ITT	intent-to-treat			
IXRS	Interactive Voice/Web Response System			
LDH	lactate dehydrogenase			
LMCI	late mild cognitive impairment			
LTE	long-term extension			
LOCF	last observation carried forward			
MCI	mild cognitive impairment			
MCMC	Markov chain Monte Carlo			
MedDRA	Medical Dictionary for Regulatory Activities			
MMRM	mixed-model repeated measures			
MMSE	Mini-Mental State Examination			
MOCA	Montreal Cognitive Assessment			
mPDQ-20	Perceived Deficits Questionnaire-20 modified version			
MRI	magnetic resonance imaging			
NIA-AA	National Institute on Aging-Alzheimer's Association			
NPI-10	Neuropsychiatric Inventory-10			
PCS	potentially clinically significant			
PET	positron emission tomography			
рН	potential of hydrogen			
PI	Principal Investigator			
PK	pharmacokinetic(s)			
PMM	pattern mixture model			
PP	per-protocol			
RBANS	Repeatable Battery for Assessment of Neuropsychological			
	Status			
ROI	region of interest			
SAE	serious adverse event			
SAP	statistical analysis plan			
SD	standard deviation			
SUSAR	suspected unexpected serious adverse reaction			
SUVR	standard uptake value ratio			
TEAE	treatment-emergent adverse event			
	treatment-emergent adverse event			
ULN	upper limit of normal			
US	United States			
WHO	World Health Organization			
**110	world Health Organization			

1 DESCRIPTION OF LONG-TERM EXTENSION (LTE) OBJECTIVES AND ENDPOINTS

1.1 Tertiary LTE Objectives

- To evaluate the long-term safety and tolerability profile of aducanumab in subjects with early Alzheimer's Disease (AD).
- To evaluate the long-term efficacy of aducanumab treatment as measured by clinical, radiological, and health outcomes assessments.

[figure not shown]
1.2 Tertiary LTE Endpoints

- The incidence of adverse events (AEs) and serious adverse events (SAEs); brain magnetic resonance imaging (MRI) findings (including the incidence of amyloid related imaging abnormality-edema [ARIA-E] and amyloid related imaging abnormality-hemorrhage or superficial siderosis [ARIA-H]); and the incidence of anti-aducanumab antibodies in serum over the placebo-controlled and LTE periods of the study.
- Change in the following measures over the placebo-controlled and LTE periods of the study:
 - Clinical Dementia Rating sum of boxes (CDR-SB) score.
 - Mini-Mental State Examination (MMSE) score.
 - Alzheimer's Disease Assessment Scale-Cognitive Subscale (13 items)
 [ADAS-Cog 13 score].
 - Alzheimer's Disease Cooperative Study Activities of Daily Living Inventory (Mild Cognitive Impairment version) [ADCS-ADL-MCI score].
 - Amyloid positron emission tomography (PET) signal (in a subset of sites and subjects).
 - Neuropsychiatric Inventory-10 (NPI-10) total scores.
 - Informant-rated EuroQol health status measures (EQ-5D) index score.

1.3 Additional Exploratory LTE Objective

Final V1.0

1.4 Additional Exploratory LTE Endpoints

2 STUDY DESIGN

2.1 Study Overview

Study 221AD301 (ENGAGE) is a multicenter, randomized, double-blind, placebo-controlled, parallel-group study in subjects with early AD, including mild cognitive impairment (MCI) due to AD and a subset of mild AD, followed by an optional dose-blinded long-term extension (LTE) period of up to 5 years. Approximately 1605 subjects will be enrolled across approximately 150 centers globally. The primary study objective is to evaluate the efficacy of monthly doses of aducanumab on the CDR-SB relative to placebo. Secondary objectives include assessment of the effect of monthly doses of aducanumab on clinical progression as compared to placebo. The safety of monthly doses of aducanumab will also be evaluated. The objectives of LTE are to evaluate the long-term safety and tolerability profile of aducanumab in subjects with early AD, and to evaluate the long-term efficacy of aducanumab treatment as measured by clinical, radiological, and health-outcomes assessments.

Subjects will be randomized in a 1:1:1 ratio to 1 of the 3 treatment groups: aducanumab high dose, aducanumab low dose and placebo, with stratification based upon their apolipoprotein E4 (ApoE &4) carrier status (carrier/non-carrier) and site. During the placebo-controlled period, subjects will receive infusions of aducanumab or placebo approximately every 4 weeks for approximately 18 months (a total of 20 doses). Dose levels may be different in the same treatment group based upon subjects' ApoE &4 carrier status, and specifically, ApoE &4 carriers will receive placebo, aducanumab 3 mg/kg, or aducanumab 10 mg/kg whereas ApoE &4 non-carriers will receive placebo, aducanumab 6 mg/kg, or aducanumab 10 mg/kg. Aducanumab will be titrated for up to 6 doses prior to reaching the target dose as shown in

Final V1.0

Table 1 and Figure 1. Note: As of Protocol Version 4, 10 mg/kg is the target dose for all ApoE ε4 carriers in the high-dose group. ApoE ε4 carriers who were randomized to the high dose group when the target dose was 6 mg/kg (under protocol versions prior to Version 4) must have received 2 or more doses at 6 mg/kg prior to being titrated up to 10 mg/kg.

Table 1: Dosing Scheme for Aducanumab by Treatment Group and ApoE ε4 Carrier Status: Placebo-controlled Period

Dose (every 4 weeks)		1	2	3	4	5	6	7 to 20
Treatment Group Stratified by ApoE Status ²		Dose (mg/kg)						
High Dose	High Dose - ApoE ε4 (+)	1	1	3	3	6	6	10 ¹
	High Dose - ApoE ε4 (-)	1	1	3	3	6	6	10
Low Dose	Low Dose - ApoE ε4 (+)	1	1	3	3	3	3	3
	Low Dose - ApoE ε4 (-)	1	1	3	3	3	3	6
Placebo	Placebo - ApoE ε4 (+)	saline						
	Placebo - ApoE ε4 (-)	saline						

¹ 10 mg/kg is the target dose for all ApoE ε4 carriers assigned to the aducanumab high-dose group. Subjects enrolled under protocol versions 1-3 and assigned to the previous high-dose of 6 mg/kg will be titrated to 10 mg/kg upon receipt of at least 2 doses at 6 mg/kg.

At the end of the double-blind, placebo-controlled treatment period, subjects who meet the extension entry criteria may enter a long-term safety and efficacy extension period, with all subjects receiving aducanumab approximately every 4 weeks (up to a total of 65 doses over 5 years). The treatment group for the LTE period will be assigned at the same time as the randomization for the placebo-controlled period, regardless of whether a subject entering the LTE period or not. Subjects who are assigned to the placebo group during the placebo-controlled period will be assigned to 1 of 2 active treatment groups in a 1:1 ratio (aducanumab low dose: aducanumab high dose) and randomization will be stratified by their ApoE ε4 carrier status; for those who enter the LTE period, aducanumab will be titrated for up to 6 doses prior to reaching the target dose following the same schedule described for the placebo-controlled period. Subjects who are assigned to either aducanumab low dose or aducanumab high dose group in the placebo-controlled period will continue in the same treatment group for the LTE period; those who enter the LTE period will maintain the dosing scheme outlined in the protocol at the time of transition from the placebo-controlled period to the LTE period (e.g. subjects who are on stable dosing in the placebo-controlled period will continue on the same dose, subjects who are on a titration regimen during the transition will continue to titrate into the LTE period, and ApoE & carrier subjects who are enrolled in the LTE and randomized to the high-dose group prior to implementation of version 4 of the protocol will be allowed to titrate to 10 mg/kg). Aducanumab will be titrated for up to 6 doses prior to reaching the target dose for the late start subjects as shown in Table 2 and Figure 1.

² ApoE ε4 status recorded in the Interactive Voice/Web Response System (IXRS).

Final V1.0

Table 2: Dosing Scheme for Aducanumab by Treatment Group and ApoE ε4 Carrier Status: Long-Term Extension Period

Doses (every 4 weeks)		1	2	3	4	5	6	7- EOS	
LTE Treatment Group	LTE Treatment Group Stratified by ApoE Status ¹	Dose (mg/kg)							
Early Start High	Early Start High Dose – ApoE ε4 (+)	10							
Dose	Early Start High Dose – ApoE ε4 (-)	10							
Early Start Low	Early Start Low Dose – ApoE ε4 (+)	3							
Dose	Early Start Low Dose – ApoE ε4 (-)	6							
Late Start High	Late Start High Dose – ApoE ε4 (+)	1	1	3	3	6	6	10	
Dose	Late Start High Dose – ApoE ε4 (-)	1	1	3	3	6	6	10	
Late Start Low	Late Start Low Dose – ApoE ε4 (+)	1 1 3							
Dose	Late Start Low Dose – ApoE ε4 (-)	1	1	3	3	3	3	6	

¹ ApoE ε4 status recorded in the Interactive Voice/Web Response System (IXRS).

[figure not shown]
Individual dose adjustments may be implemented in subjects who develop amyloid related imaging abnormalities (ARIA). See Protocol Section 7.2.1.

The total duration of study participation for each subject only participating in the placebo-controlled period of the study will be up to approximately 102 weeks, including a series of screening visits within 8 weeks before administration of the first dose, a 76-week placebo-controlled treatment period, and a safety follow-up (FU) period of approximately 18 weeks after the final dose. The total duration of study participation for each subject participating in the placebo-controlled period and the LTE period will vary and be up to approximately 362 weeks, including a series of Screening visits within 8 weeks before administration of the first dose, a 76-week placebo-controlled treatment period, a 4-week FU period, a 256-week aducanumab dose-blind treatment period, and a safety FU period of approximately 18 weeks after the final dose.

Investigators, study site staff (except for the designated unblinded pharmacist/technician), and study subjects will be blinded to the subjects' randomized treatment assignment for the placebo-controlled period. During the LTE period, investigators and subjects will remain blinded to the treatment assignment in the placebo-controlled period and the aducanumab dose for the LTE period.

